4.5. Safety Analyses

The MITT- population will be used for the analysis of safety data.

AEs will be considered on-treatment for at least 4 weeks (28 days) following the last dose of study treatment, AEs which occur more than 28 days following the last dose of study treatment will be considered as post-treatment, the detailed definition can be found in Section 6.2.3. All primary safety analysis will use the “While on Treatment” approach, i.e. any safety events which occur post discontinuation of study intervention will be excluded. For key safety outputs, post-treatment data will be included in analysis or displayed separately, detailed information will be defined in the following sections. The listings will cover all of pre-, on- and post- treatment data.

Generally, the missing data will not be imputed, except the AE severity and relatedness data. If an adverse event severity is missing, the severity is to be populated as ‘UNKNOWN’. A worst-case scenario approach will be taken to handle missing relatedness data, i.e. the summary table will include events with the relationship to study treatment as ‘Yes’ or missing.

4.5.1. Extent of Exposure

IP is administered approximately every 4 weeks and each dose viewed as providing therapeutic coverage for 4 weeks (28 days). Duration of exposure in months is calculated based on the therapeutic coverage as follows:

$$\text{Duration of Exposure (months)} = (\text{IP Stop Date} - \text{IP Start Date} + 29) * 12/365.25$$

Subject years exposure is calculated as follows:

$$\text{Subject Years Exposure} = (\text{IP Stop Date} - \text{IP Start Date} + 29)/365.25$$

If the IP start date is missing and there is evidence the subject received at least one dose of IP, the IP start date will be taken to be the date of randomisation, and if the IP end date is missing it will be taken to be the last on-treatment visit attended.

Randomised subjects with no evidence of receiving at least one dose of IP will be shown as having zero days of exposure.

In addition, the number of subjects administered investigational product, the number of treatments administered, and the number of days over which treatment was administered will be summarized.

4.5.2. Adverse Events

Adverse events will be summarized by system organ class and preferred term . AEs will be summarized for on-treatment period, unless otherwise specified.

The number and percentage of subjects experiencing at least one AE during on-treatment period of any type, AEs within each body system and AEs within each preferred term will be summarized for each treatment group.

- Overview of all AEs

The following summary tables will be produced:

- Summary of all AEs; (on-treatment, post-treatment)
- Summary of drug related AEs;
- Summary of Common ($\geq 3\%$ Incidence in any Treatment Group) Adverse Events by Overall Frequency
- Summary of AEs by maximum intensity
- Summary of Severe AEs (on-treatment, post-treatment)
- Summary of SAEs; (on-treatment, post-treatment)
- Summary of non-SAEs
- Summary of Common ($\geq 3\%$ Incidence in any Treatment Group) Non-Serious Adverse Events by Overall Frequency (on-treatment)
- Summary of drug related SAEs (on-treatment)
- Summary of non-fatal SAEs (on-treatment)
- Summary of Fatal Events (on-treatment, post-treatment)
- Summary of Adverse Events Leading to Permanent Discontinuation of Study Drug or Withdrawal from Study
- Summary of Adverse Events Leading to Interruption of Study Drug
- Summary of AEs by ADA Assay Result Category (On-Treatment)
- Summary of AEs by NAb (On-Treatment)

The following listings will be produced:

- Listing of Subject Numbers for Individual Adverse Events
- Listing of all Adverse Events
- Listing of Non-Fatal Serious Adverse Events
- Listing of Fatal Adverse Events
- Listing of Adverse Events Leading to Discontinuation of Investigational Product and/or Withdrawal from the Study

Exposure Adjusted Rate for Adverse Events

Exposure adjusted rate for adverse events represents the frequency of events per 1000 subject-years of exposure, which is calculated as:

(Total number of adverse events / Total Duration of Exposure in days)/365.25*1000

The summary of exposure adjusted for the events below will be provided:

- All Adverse Events (on treatment)
- Most frequent AEs reported by 3% or more subjects (on treatment)
- Drug related AEs (on treatment)
- Non-fatal SAEs (on treatment)

- Adverse Events Leading to Permanent Discontinuation of Study Drug or Withdrawal from Study (on treatment)

Adverse Events of Special Interest

Systemic reactions and local injection site reactions are adverse events of special interest (AESIs) which are collected using target eCRF pages within the study, and will be summarized separately. The summary of symptoms associated with AEs defined by the investigator as being systemic/local injection site reactions will be displayed.

AESIs of potential opportunistic infections, malignancies, serious cardiac, vascular and thromboembolic (CVT) events and serious ischemic events will be identified from a list of relevant preferred terms maintained within a project level reference dataset created based on the latest version of the MedDRA dictionary available at the time of source data lock for this study. Further details of how relevant preferred terms are identified for the AESIs are given in the Program Safety Analysis Plan (PSAP).

Separate summary tables showing the number and percent of participants with each type of AESI, broken down by preferred term will be created. These summaries will be reported as part of the standard AE/SAE tables for the AESIs of infections, serious infections, neoplasms, cardiac disorders and serious cardiac disorders. The relative risk and risk difference of each AESI between mepolizumab and placebo will be presented with 95% confidence intervals.

For each AESI a profile summary table will be produced containing information on event characteristics including, but not be limited to, the number of participants with the AESI, the number of occurrences of the AESI, the number of participants with a serious event or a drug related event, maximum severity, outcome and action taken.

COVID-19 Assessment and COVID-19 AEs

Listing of COVID-19 assessment and COVID-19 AEs will be provided.

Impact of COVID-19 Pandemic on Safety Results

The impact of the COVID-19 pandemic on the safety results will be assessed. Pandemic measures began in different countries at different times. The start date of pandemic in China was Jan. 24th. 2020, which was determined by the GSK country Issue Management Teams (IMT), will be used in the following summaries.

Summaries of the incidence rates of AEs, SAEs and severe AEs, before (AE onset date < pandemic measure start date) and after (AE onset date >= pandemic measure start date) the start of the COVID-19 pandemic will be produced.

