5.5. Withdrawal/Stopping Criteria

Withdrawal from study treatment

Subjects may be withdrawn from study treatment at anytime by the Investigator if it is considered to be detrimental for them to continue in study treatment.

A subject must be withdrawn from study treatment if any of the following stopping criteria are met:

- Liver Chemistry: Meets any of the protocol-defined liver chemistry stopping criteria (Section 5.5.1)
- QT: Meets any of the protocol-defined stopping criteria (Section 5.5.2)
- Pregnancy: Positive pregnancy test

Other reasons for withdrawal can include: an adverse event (including abnormal liver function test other than stopping criteria or abnormal laboratory results), Investigator unblinded study treatment, clinically significant abnormality identified on ECG reading other than stopping criteria, lost to follow-up, protocol violation, lack of efficacy, sponsor terminated study, non-compliance, or for any other reason.

Subjects who withdraw from study treatment prematurely (for any reason) should, where possible, continue to be followed-up as per protocol until the completion of the Exist Visit assessments. If this is not possible, the Investigator must encourage the subject to participate in as much of the study (scheduled visits and activities, record eDiary data) as they are willing (or able) to. If subject cannot attend the visit on site, telephone contact is acceptable to collect below information: asthma exacerbation, AE/SAE, concomitant medication and to encourage subjects continue to record eDiary data.

Withdrawal from the study

Subjects are also free to withdraw consent to participate in the study at anytime. Every effort should be made to have them return to the clinic for an Early Withdrawal Visit and to return all study related materials. In those instances where the subject specifies the reason for withdrawal of consent, this information will be captured in the eCRF. Patients will not be followed for any reason after consent has been withdrawn.

A subject should only be designated as lost to follow-up if the site is unable to establish contact with the subject after 3 documented attempts via 2 different methods (phone, text, e-mail, certified letter, etc).

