4.5.3. Additional Safety Assessments

Cardiovascular events

The following cardiovascular events on treatment will be summarised and listed:

- Myocardial infarction/unstable angina
- Congestive heart failure
- Arrhythmias
- Valvulopathy
- Pulmonary hypertension
- Cerebrovascular events stroke and transient ischemic attack
- Peripheral arterial thromboembolism
- Deep vein thrombosis/pulmonary embolism
- Revascularization

Laboratory Data

The change from baseline values on- and post- treatment for clinical chemistry and haematology will be summarised. Summaries of the data outside the normal range and the changes from baseline relative to the normal range will also be produced, including 'any time post-baseline', which will include laboratory assessments taken at scheduled, unscheduled and Early Withdrawal visits and will report the most extreme value(s). Data from subjects who have values outside the normal range will be listed.

Urinalysis results (screening only) will be listed.

Vital Signs

Pre-dose systolic blood pressure, diastolic blood pressure and pulse rate including change from baseline for on- and post- treatment will be summarised and listed.

ECG

Actual and change from baseline (for post-baseline timepoints) values for QTc(F) and heart rate including on- and post- treatment will be summarised by treatment for Baseline, Week 24, Week 52 and Withdrawal visit. ECG results will also be listed. Abnormal findings and interpretations will be listed separately.

Individual maximum QTc(F) values will also be summarised to show the number of subjects with maximum values (msec) in the following categories:

- ≤ 450
- $450 < \text{to } \leq 480$
- $480 < \text{to } \leq 500$
- > 500

Additionally, individual maximum changes from baseline in QTc(F) values will be summarised to show the number of subjects with maximum changes (msec) in the following categories:

- Increase of <=30 msec
- Increase of >30-<=60 msec
- Increase of >60 msec

Liver Event

Liver event information on- and post- treatment will be summarised and all subjects who report a liver event will be listed.

Immunogenicity

For the immunogenicity assessment, two types of anti-drug antibody (ADA) assays will be performed: a binding antibody assay and a neutralizing antibody assay (NAb).

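### AESI risk estimates for malignancy, serious CVT and serious ischaemic events fall under the on-treatment default, and the cardiovascular-event listing contradicts SAP 4.5

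*SAP*

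**What the plan says.** SAP 4.5 takes a while-on-treatment approach for the primary safety analysis and places the boundary as follows: "AEs which occur more than 28 days following the last dose of study treatment will be considered as post-treatment". SAP 6.2.3 gives the same window for adverse events, applied to the event start date. SAP 4.5 then makes a general promise: "For key safety outputs, post-treatment data will be included in analysis or displayed separately, detailed information will be defined in the following sections".

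SAP 4.5.2 keeps that promise for some outputs. The default is "AEs will be summarized for on-treatment period, unless otherwise specified". Post-treatment versions are named for all AEs, severe AEs, SAEs and fatal events. For the AESIs it says: "The relative risk and risk difference of each AESI between mepolizumab and placebo will be presented with 95% confidence intervals". No period is given there.

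SAP 4.5.3 is explicit for the events captured on the cardiovascular pages: "The following cardiovascular events on treatment will be summarised and listed". SAP 4.5 says of listings in general: "The listings will cover all of pre-, on- and post- treatment data".

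On data collection, Protocol 5.5 provides that subjects who stop study treatment early "should, where possible, continue to be followed-up as per protocol until the completion of the Exist Visit assessments". If they cannot attend, AE and SAE information may be taken by telephone.

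**The concern.** Protocol 2.3.1 names cardiovascular effects and malignancies as potential risks. For the first it mentions a small numerical excess of serious cardiac events in one earlier Phase III study, which an integrated analysis did not confirm. These are the risks for which the SAP plans a between-arm estimate, and malignancy in particular has no obvious reason to be counted only up to 28 days after a dose.

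The study plans to keep observing subjects who stop treatment, so later events will be in the database. If the AESI estimates follow the default, that follow-up contributes nothing to them. The AESI tables are specified as numbers and percentages of participants, and none of the exposure-adjusted summaries in SAP 4.5.2 is for an AESI. If early stopping differs between arms, the time at risk behind the two percentages will also differ, and no planned AESI output shows it.

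The listing conflict is separate and simpler: a programmer cannot satisfy both SAP 4.5 and SAP 4.5.3 for the cardiovascular events.

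**Working it through.** **Text check**

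| Output | Period in the SAP | Post-treatment data shown? |
|---|---|---|
| All AEs, severe AEs, SAEs, fatal events (4.5.2) | On- and post-treatment, separately | Yes |
| Chemistry and haematology, vital signs, ECG, liver events (4.5.3) | On- and post-treatment | Yes |
| AESI relative risk and risk difference (4.5.2) | Not stated, so the default applies | No |
| Cardiovascular-event summary (4.5.3) | On treatment, stated | No |
| Cardiovascular-event listing | On treatment (4.5.3); all periods (4.5) | Contradictory |

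The window is also unclear within SAP 4.5, which says that "any safety events which occur post discontinuation of study intervention will be excluded" while counting 28 days after the last dose as on-treatment.

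**Size of the follow-up outside the window**

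The plan gives no figure for this, so there is nothing to reproduce. The inputs are:
- 300 subjects randomised, 52 weeks of treatment, doses every 4 weeks from Week 0 to Week 48 (Protocol 4.2).
- 44 subjects allowed for early withdrawal from study treatment (Protocol 9.2.2): 44/300 = 14.7%.
- On-treatment ends at last dose + 4 weeks (SAP 6.2.3).
- Assumptions: every early stopper remains in the study to Week 52, and total planned follow-up is 300 subject-years.

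For a subject whose last dose is at week d, the time outside the window is 52 − (d + 4) weeks. Over d = 0, 4, …, 44 this runs 48, 44, …, 4, with a mean of 26 weeks.

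| Early stoppers | Timing of last dose | Subject-years outside | Share of 300 |
|---|---|---|---|
| 44 | Spread evenly over Weeks 0–44 | 44 × 26/52 = 22.0 | 7.3% |
| 44 | All at Week 44 | 44 × 4/52 = 3.4 | 1.1% |
| 44 | All at Week 0 | 44 × 48/52 = 40.6 | 13.5% |
| 15 | Spread evenly | 15 × 26/52 = 7.5 | 2.5% |

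Completers add almost nothing. Week 48 + 28 days is Week 52, so at most the 7-day visit allowance falls outside.

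**Events**

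The documents give no AESI rates. Purely for scale, assume a constant rate of 0.5 to 2 per 100 subject-years. Then 1.5 to 6.0 events would be expected in 300 subject-years, and 0.11 to 0.44 of them in the 22 subject-years outside the window. This says nothing about the direction or size of any change in relative risk.

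**The case against.** Four points on the other side have force.

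1. **The late events are not lost.** Serious CVT and serious ischaemic events are serious by definition, and Protocol Appendix 3 gives invasive or malignant cancers as examples of serious events. They would appear in the post-treatment SAE table. SAP 4.5.2 also ties the neoplasm and cardiac-disorder summaries to the standard AE/SAE tables, and the general rule puts all periods in the listings. This stands. What is missing is a between-arm AESI estimate that includes these events.

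2. **Classification is by start date.** A reader might infer that a cancer or cardiac event diagnosed after the cut is dropped, and hence that events prompting discontinuation are systematically missed. SAP 6.2.3 does not support that. An event with onset inside the window counts as on-treatment whenever it is confirmed, and a missing event start date or missing treatment stop date also counts as on-treatment. AEs leading to discontinuation have their own summary. Only events that start after the cut are affected.

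3. **The AESI paragraph does not itself say on-treatment.** Correct. That reading follows from the default rule; only the cardiovascular-event sentence in SAP 4.5.3 says it outright.

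4. **Separation by period is protocol policy.** Protocol 9.4.2.2 calls for separate summaries by treatment period, and SAP 4.5.1 views each dose as covering 4 weeks. This justifies keeping the on-treatment tables as the main display. It does not preclude a supplementary estimate over all collected follow-up.

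It is also tempting to argue from residual drug at 28 days. SAP 4.7.1 refers to about five half-lives in a missed-dose rule but states no half-life, so any figure would be back-calculated from visit spacing. The point does not need it.

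**Conclusion.** The concern holds in a limited form. Under the SAP's default, the AESI relative risks and risk differences for malignancies, serious CVT and serious ischaemic events count only events starting up to 28 days after the last dose, and no estimate over all collected follow-up is planned. For the cardiovascular-event listing, SAP 4.5.3 and SAP 4.5 contradict each other and must be reconciled.

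The follow-up left out is about 7.3% of planned subject-years in the evenly spread case, 1.1% to 13.5% depending on when subjects stop, and 2.5% with 15 evenly spread early stoppers. These figures assume that everyone who stops treatment stays to Week 52. Protocol 9.2.1 describes the 44 as drop-outs, and Protocol 5.5 promises follow-up only where possible and none after consent is withdrawn, so for a given number of early stoppers the true amount will be smaller if some leave.

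A reader might conclude that the planned AESI estimates are biased in favour of mepolizumab. The documents do not show that: they give neither AESI rates nor arm-specific discontinuation, so neither the direction nor the size of any change can be computed. This is a modest gap that is cheap to close.

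**What to change.** In SAP 4.5.2:
- Keep the on-treatment AESI tables and state their period, which would also settle the unclear wording in SAP 4.5.
- For malignancies, serious CVT and serious ischaemic events, add a supplementary version over all collected follow-up (on- plus post-treatment), with the same relative risk and risk difference and their intervals.
- Show follow-up time by arm beside it.

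In SAP 4.5.3:
- Let the cardiovascular-event listing cover all periods, in line with SAP 4.5.
- Add a post-treatment row to the cardiovascular-event summary, as the same section already does for laboratory data, vital signs, ECG and liver events.

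The cost is SAP wording and a few extra outputs from data already being collected; treatment, visits and case report forms are unchanged. The downside is that some of the added events will be unrelated to drug, which is why the on-treatment estimate should stay as the main one and the all-follow-up version be labelled supplementary.

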4.3. Type and Number of Subjects

Approximately 429 subjects will be screened to achieve 300 randomized at a ratio of 1:1 (150 subjects in mepolizumab arm and 150 subjects in placebo arm).

This study will include a PK sub-study in which approximately 52 randomized subjects will provide PK samples, irrespective of the allocated treatment (to maintain the study blind). This will ensure approximately 26 subjects receiving mepolizumab will provide PK information. This is to meet the regulatory requirement of approximately 20 evaluable subjects for PK analysis.

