6.2.4. Length of Time in Phase for Exacerbations

The length of time in a phase reflects for each subject the period of time over which exacerbation data has been recorded and included in the negative binomial analysis model. The analysis model will incorporate this information as an offset of loge (length of time (years) in phase).

Length of time (years) will be calculated as Length of time (Days)/365.25.

The length of time a subject contributes information in each phase is detailed below.

Phase	Length of time (Days) in Phase
On- and Off-treatment	(Date of End of Analysis Period – IP Start Date) +1
On-treatment	Subjects who did not withdraw early from IP: (Date of End of Analysis Period – IP Start Date) +1 Subjects who withdrew early from IP: (IP Stop Date – IP Start Date) +28+1
Off-treatment	Subjects who did not withdraw early from IP: 0 days Subjects who withdrew early from IP: Date of End of Analysis Period – [IP Stop Date + 28 days]

Subjects who withdraw early from the study with an analysis period which ends prior to Day 372 will be considered to have missing data for a period of time calculated as: (Day 372-Date of End of Analysis Period) +1.

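### The exposure-adjusted adverse event formula divides by 365.25 where it should multiply, so the planned rates per 1000 subject-years come out too small by a factor of about 133,000

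*SAP*

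**What the plan says.** SAP section 4.5.2 states the unit in words: "Exposure adjusted rate for adverse events represents the frequency of events per 1000 subject-years of exposure". The formula that follows is "Total number of adverse events / Total Duration of Exposure in days)/365.25*1000", with the opening bracket immediately before the quoted text. It applies to five on-treatment summaries listed beneath it: all adverse events, events reported by 3% or more of subjects, drug-related events, non-fatal serious events, and events leading to permanent discontinuation of study drug or withdrawal from the study.

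The SAP converts days to years in two other places. In section 4.5.1, subject-years are (IP stop date − IP start date + 29)/365.25, where the 29 reflects "each dose viewed as providing therapeutic coverage for 4 weeks (28 days") plus the first day. In section 6.2.4, for the exacerbation offset, "Length of time (years) will be calculated as Length of time (Days)/365.25".

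Protocol section 9.4.2.2 (Adverse Events) gives no formula for this rate, so SAP 4.5.2 is its only specification.

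**The concern.** Events divided by days of exposure is a rate per day. A yearly rate is 365.25 times larger, yet the formula makes it 365.25 times smaller. The bracket closes before the division, so the 365.25 cannot be read as converting the denominator into years. The formula therefore cannot produce the unit that the preceding sentence gives it.

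If it is programmed literally, five safety tables would carry a label of events per 1000 subject-years over values that are not in that unit. Absolute rates and rate differences would be unusable as labelled, and a reader setting them beside properly computed rates from another study would be misled. Independent double programming would not protect against this, since both programmers would work from the same line.

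**Working it through.** The documents report no numerical rate, so there is no figure to reproduce. The check is of units, followed by arithmetic.

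**Inputs**
- Stated unit: events per 1000 subject-years (SAP 4.5.2).
- Formula as written (SAP 4.5.2).
- Conversion: subject-years = days / 365.25 (SAP 4.5.1; same conversion in SAP 6.2.4).
- For illustration only: 150 subjects per arm (Protocol 4.3).

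**Formulas.** Let E be the total number of events and D the total exposure in days.
- As written: R_w = (E/D) / 365.25 × 1000
- From the stated unit: R_c = E / (D/365.25) × 1000 = (E/D) × 365.25 × 1000
- Ratio: R_c / R_w = 365.25 × 365.25 = 133,407.56

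E and D cancel, so the factor is the same for every table, arm and event type.

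**Unit check.** One event in one subject-year (D = 365.25) should give 1000.
- As written: (1/365.25) / 365.25 × 1000 = 0.0075
- Correct: 1 / (365.25/365.25) × 1000 = 1000

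**Illustrations.** The event counts are assumptions; neither they nor the total exposures are in the documents.

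| Scenario | E | D (days) | Subject-years | As written | Correct |
|---|---|---|---|---|---|
| One arm, 150 subjects × 365 days | 300 | 54,750 | 149.9 | 0.0150 | 2001 |
| Both arms pooled | 1000 | 109,575 | 300 | 0.0250 | 3333 |
| One preferred term in one arm | 10 | 54,787.5 | 150 | 0.0005 | 66.7 |

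The 365 days in the first row are 336 days from first to last dose (48 weeks × 7) plus the 29 of SAP 4.5.1. Taking 364 days instead gives D = 54,600 and rates of 0.0150 and 2007; the ratio does not move.

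**Alternative reading.** If the tail is read as division by (365.25 × 1000), the result is smaller still: the ratio becomes (365.25 × 1000)² ≈ 1.33 × 10¹¹. Left-to-right evaluation is the more favourable reading, and it is the one used above.

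**The case against.** The error, its factor and the absence of any correcting text elsewhere are not in dispute. The case on the other side concerns how much it matters.

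- **Probably a misplaced bracket that would be noticed.** The unit is stated in words directly above the formula, and the correct subject-years are defined in the section before. An alert programmer would see that one event in one subject-year gives 0.0075. This is plausible, and the error in the tables does depend on literal coding. But a silent correction would be an undocumented departure from the written plan, which is a reason to amend the text.
- **No inference depends on it.** This stands. The multiplier is the same in both arms, so between-arm ratios of these rates are unchanged. The main adverse event tables are counts and percentages of subjects, and the relative risks and risk differences for events of special interest accompany tables of that kind. The exacerbation model uses the correct offset, and the primary success criterion is untouched.
- **The values would not necessarily print as zero.** This also stands in part. SAP 4.1.1 allows up to four decimals and fixes no precision for event rates. The pooled value of 0.0250 prints as 0.0 at one decimal and 0.02 at two. A single-term rate of 0.0005 prints as zero at up to three decimals.
- **A known constant can be reversed.** True, but only by a reader who has noticed the error, and not for entries already rounded to zero.

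These points limit the consequences. None of them makes the formula right.

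**Conclusion.** The concern holds. As written, the formula in SAP 4.5.2 contradicts its own stated unit and the conversion used in SAP 4.5.1 and 6.2.4. Each exposure-adjusted rate would be too small by 365.25² = 133,408, assuming the formula is coded literally and evaluated left to right. The factor needs no assumption about event counts or exposure.

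The damage is confined to the absolute level, and differences in level, of the five exposure-adjusted adverse event summaries. It is nonetheless a prespecified rule that gives a wrong result when followed, and it should be corrected before those tables are programmed.

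**What to change.** Replace the formula in SAP 4.5.2 with:

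Total number of adverse events / (Total duration of exposure in days / 365.25) × 1000

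Equivalently, divide the events by the summed subject-years of SAP 4.5.1 and multiply by 1000. It would help to state that the exposure days are IP stop date − IP start date + 29, summed over the subjects in the treatment group, so that the denominator is tied explicitly to SAP 4.5.1. If any of the five tables has already been programmed, test the code with one event in 365.25 days, which must return 1000.

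The cost is one line of SAP text. Design, data collection and all other analyses are unchanged, and there is no downside.
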